## 6.8 Assessment of Investigational Medicinal Product Compliance

The IMP will be administered at the site on the trial visit days defined in [Table 1](#). All other dosing will be done by the patient or patient's caregiver at home throughout the rest of the trial. Patients will be asked to record the date and time dispensed, date and time of dosing, location of administration, and injection site reaction (yes/no) in a patient diary. Diaries will be collected and reviewed at the trial visits specified in [Table 1](#).

Patients will be instructed to bring all IMP, including the used packaging, to each trial visit to allow for the assessment of compliance with trial treatment. Prior to discharge from each scheduled visit, patients will be given sufficient IMP for at-home dosing until the next scheduled visit.

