- Study Drug Related Injection Site Reactions by NCI-CTCAE grade and duration
- Study Drug Related Injection Site Reactions by NCI-CTCAE grade and time since last study administration

Summary statistics will be presented for the following:

MSB11022 in Moderate to Severe Rheumatoid Arthritis version 3.0 Final

- Duration of study drug related injection site reactions (hours) calculated as the difference of start date/time and stop date/time divided by 3600 [(stop date/time start date/time)/3600]. If start time is missing then start time will be set to 00:00. If stop time is missing then stop time will be set to 23:59. Duration will not be calculated if start date or stop date are missing. If a subject has more than one study drug related injection site reactions then the event with the longest duration will be used.
- Number of subjects with duration of study drug related injection site reaction <24 hours, ≥ 24 < 48 hours and ≥ 48 hours. If a subject has more than one study drug related injection site reactions then the event with the longest duration will be used.
- Time since the first study treatment administration to the study drug related injection site reaction start date/time calculated as the difference of first study drug administration date/time and the injection site reaction start date/time divided by 3600 [(Injection site reaction start date/time First study drug administration date/time)/3600]. Time since the first study treatment administration will not be calculated if injection site reaction start date or first study drug administration date are missing. If first study treatment administration time is missing then it will be set to 23:59. If study drug related injection site reaction start time is missing then it will be set to 00:00. In the special cases that any time is missing and first study treatment administration date equals the study drug related injection site reaction start date then time since first study treatment administration will be set to 0. If a subject has more than one study drug related injection site reactions then the event with the shortest duration will be used.
- Number of subjects with time since the first study treatment administration to the study drug related injection site reaction <24 hours, ≥ 24 < 48 hours and ≥ 48 hours. If a subject has more than one study drug related injection site reactions then the event with the shortest duration will be used.

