- Time since last study treatment administration to the study drug related injection site reaction start date/time calculated as the difference of the last study drug administration date/time and the study drug related injection site reaction start date/time divided by 3600 [(Injection site reaction start date/time Last study drug administration date/time)/3600]. Time since the last study treatment administration will not be calculated if study drug related injection site reaction start date or last study drug administration date are missing. If last study treatment administration time is missing then it will be set to 23:59. If injection site reaction start time is missing then it will be set to 00:00. In the special cases that any time is missing and last study treatment administration date equals injection site reaction start date then time since last study treatment administration will be set to 0. If a subject has more than one study drug related injection site reactions then the event with the shortest duration will be used.
- Number of subjects with time since the last study treatment administration to the injection site reaction <24 hours, ≥ 24 < 48 hours and ≥ 48 hours. If a subject has more than one study drug related injection site reactions then the event with the shortest duration will be used.
- Medication or procedure taken for study drug related injection site reactions. Frequencies and percentages will be based on the number of subjects.

Additionally the study drug related injection site reactions rate based on the overall number of study treatment injections administered will be calculated by SOC and PT.

The following frequency tales will be prepared by PT in order of decreasing frequency across both treatment arms:

- TEAEs with frequency of $\geq 5\%$ in any treatment arm
- TEAEs with frequency of $\geq 1\%$ in any treatment arm
- Treatment emergent AESIs (as per section 15.1).

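### SAP 16.1.1 gives a date-only injection site reaction a duration set by the midnights it crosses, which overstates the hours and can move it up one category

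*SAP*

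**What the plan says.** SAP 16.1.1 (All Adverse Events) derives the duration of each drug-related injection site reaction as stop date/time minus start date/time, in hours. Its rules for incomplete data are:

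- Start: "If start time is missing then start time will be set to 00:00".
- Stop: "If stop time is missing then stop time will be set to 23:59".
- Dates: "Duration will not be calculated if start date or stop date are missing".
- Several reactions in one subject: "then the event with the longest duration will be used".

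The outputs are summary statistics in hours and a categorical count, "Number of subjects with duration of study drug related injection site reaction <24 hours", with further classes of 24 to under 48 hours and 48 hours or more. A table by toxicity grade and duration is also planned.

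The same section derives latency from the first and from the last dose. There too, "If injection site reaction start time is missing then it will be set to 00:00", but with an extra rule: if any time is missing and the dose and reaction share a date, latency is set to 0.

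On data capture, Protocol 6.8 has patients note "date and time of dosing, location of administration, and injection site reaction (yes/no) in a patient diary". Protocol 7.4.2.2 asks that AE reports give onset and resolution dates, with clock times where timing relative to dosing matters. Table 1, footnote t, asks patients to record when injection site pain resolves if it lasts beyond one hour at doses 3 to 5.

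**The concern.** The rule takes the earliest possible start and the latest possible stop, so every error lengthens the reaction. The imputation unit is a whole day at each end, and the categories are only 24 hours wide. The reported figure can therefore say more about calendar dates than about the reaction.

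Two features add to this. On a dosing day a start at 00:00 lies before the injection that caused the reaction. The latency rules deal with that case; the duration rule does not. And because the longest event per subject is chosen from durations derived in this way, an inflated value tends to displace a correctly timed one.

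At stake is the reading of the duration part of the local tolerability summaries. The documents name injection site reactions among the most common AESIs (Protocol 8.1, SAP 7.1), so these tables will be looked at.

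**Working it through.** The plan states no duration figure to reproduce. The check applies its rule directly.

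**Inputs.** From SAP 16.1.1: missing start = 00:00, missing stop = 23:59, cut points 24 h and 48 h. Let k be the number of midnights crossed (stop date minus start date), s the true clock time of onset and e the true clock time of the end.

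**Formulas, both times missing.**
- Imputed duration = 24k h + 23 h 59 min.
- True duration = 24k + e − s.
- Overstatement = s + (23 h 59 min − e).

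The imputed value does not contain s or e, so it carries no information beyond k.

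**Results by k.** The averages assume s and e uniform over the day and independent, with the earlier taken as onset when k = 0. That is my assumption, not the documents'.

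| k | Imputed | Class assigned | Possible true duration | Overstatement (mean) | Wrong class |
|---|---|---|---|---|---|
| 0 | 23 h 59 min | <24 h | 0 to 24 h | 0 to 24 h (16 h) | none |
| 1 | 47 h 59 min | 24 to <48 h | 0 to 48 h | 0 to 48 h (24 h) | about 50% |
| 2 | 71 h 59 min | ≥48 h | 24 to 72 h | 0 to 48 h (24 h) | about 50% |
| 3 | 95 h 59 min | ≥48 h | 48 to 96 h | 0 to 48 h (24 h) | none |

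For k = 1 the true duration is below 24 h whenever e < s, which has probability one half. The same condition puts a k = 2 reaction below 48 h. Larger k behaves like k = 3.

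**Example.** Onset 20:00, end 08:00 next day: true duration 12 h. Imputed: 00:00 on day 1 to 23:59 on day 2 = 47 h 59 min, one class too high.

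**One time missing.** The mean overstatement is about 12 h when the dates differ and about 8 h on a single date. When one or two midnights are crossed, about half of the reactions still change class.

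**By true duration d, both times missing.** For d below 24 h the class is wrong exactly when the reaction crosses midnight.
- Onset uniform over 24 h: probability d/24. This gives 1/24 = 4%, 6/24 = 25%, 12/24 = 50%, 20/24 = 83%.
- Onset uniform from 08:00 to 20:00 (also assumed): 0% at 1 h; 2/12 = 17% at 6 h; 8/12 = 67% at 12 h; 100% at 20 h.

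The size therefore depends strongly on how long reactions really last, which the documents do not say.

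**Dosing day.** Take an injection at 10:00 and a reaction that starts and ends on that date, with no times. The rule gives 23 h 59 min, of which 10 h precede the injection. Starting no earlier than the injection caps it at 23:59 − 10:00 = 13 h 59 min.

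**Longest event.** Suppose a subject has one fully timed 20 h reaction and the date-only 12 h reaction above. The 47 h 59 min value is selected, and the subject is counted in 24 to <48 h although neither reaction reached 24 h.

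**The case against.** The strongest defence is that this is a pre-specified worst-case convention, applied identically in two blinded arms, for descriptive tables with no test. SAP 16.1 also takes a worst-case view of missing times when deciding treatment emergence. That largely stands. A comparison between arms is biased only if missing times, or the tendency to cross midnight, differ by arm. But worst case suits a yes/no question such as treatment emergence better than a number of hours, and nothing in the plan labels these values as upper bounds or counts them.

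Several stronger readings are tempting, and the documents do not support them.

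- *That date-only reactions generally land in the wrong class.* Same-date reactions and those crossing three or more midnights do not.
- *That the yes/no diary item means times will usually be missing.* Of 25 doses (Weeks 0 to 48, every 2 weeks), 8 fall at site visits and 17 at home, but that is a share of doses, not of reactions without times. AE reports can carry clock times, and pain resolution is recorded at doses 3 to 5. A diary tick with no AE start and stop date gets no duration at all. The longest gap from a home dose to the next visit is 10 weeks (for example Week 14 to Week 24), so recall is a fair worry, but no rate of missing times is given.
- *That latency is equally distorted.* A next-day reaction without a start time does have its latency shortened. Same-date reactions, however, are set to 0 and fall correctly under 24 hours.
- *That the primary safety result is affected.* AESI incidence, reaction counts, toxicity grades, the rate per injection and the pain VAS do not use these imputed durations.

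**Conclusion.** The point holds in a limited form. For reactions without clock times, SAP 16.1.1 produces an hour figure fixed by the calendar dates alone. It overstates by up to 24 hours on a single date and by 0 to 48 hours otherwise, about 24 hours on average under uniform clock times. Misclassification is always upward by one class and is confined to reactions crossing one or two midnights, about half of them under the same assumption. Missing the start guard that the latency rules have, and keeping the longest event, both add to the upward error.

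How much this changes the tables depends on two unknowns: the share of reactions lacking a time and the true distribution of durations. The consequence is limited to the descriptive duration summaries. It is worth correcting because the correction is cheap, not because a main conclusion depends on it.

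**What to change.** Amend SAP 16.1.1 before database lock as follows.

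1. Summarise duration in hours, and select each subject's longest event, only among reactions with both clock times recorded.
2. Classify date-only reactions by calendar days: resolved the same day, the next day, or later.
3. Wherever a start time is still imputed, do not let it fall before the recorded injection time.
4. Report by arm how many reactions had both times recorded, so that the reader can see what the hour-level figures rest on and whether missing times are balanced.

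The cost is SAP wording and table programming, with no new data. The downside is that some reactions will have no hour-level duration, and a subject's longest reaction may be known only in calendar days.

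Adding start and stop times to the home diary would have been the better source, but it comes too late here: SAP version 3.0 is dated 06 September 2018, and the protocol planned last patient out for Quarter III 2018. Mid-point imputation is possible but only swaps one assumption for another, so it is not proposed.

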11.1 Descriptive Methods

Descriptive statistics for continuous data will include the following:

- Number of subjects with non-missing data (n)
- Number of subjects with missing data
- Mean, standard deviation (SD)
- Median, first and third quartiles (Q1 and Q3)
- Minimum and maximum
- 95% confidence interval (CI).

All statistics will be rounded according to Merck's Global Biostatistics Output Standards (GBSOS) Booklet (Version 4.0 or later), ie, percentages will be rounded to one decimal. The mean, median, Q1, Q3, and 95% CI will be presented with one additional decimal compared to the raw data; SD will be presented with two additional decimals compared to the raw data; and minimum and maximum will be presented with the same number of decimals as the raw data.

All data will be presented by nominal visit (including the safety follow-up visits – four weeks and four months after the last dose of IMP) and no visit windowing rules will be implemented. Data from unscheduled visits will be listed but will not be included in summaries presented by

visit. The exceptions will be in the calculation of the baseline values. Data from unscheduled visits will also be included in the calculation of the worst on-treatment values and grades.

Categorical data will be summarized by presenting the number of subjects with non-missing data (n), the number of subjects with missing data (missing), and the number and percentage of subjects in each category. Percentages will be based on the number of subjects with non-missing data in the analysis set of interest, unless otherwise specified.

Time to event variables will be summarized by presenting Kaplan Meier estimates and 95% CIs.

Change from baseline will be calculated as the post-baseline value minus the baseline value. Percent change from baseline is defined as (100 x (post-baseline – baseline) / baseline).

If all baseline values are missing for a particular variable, the change from baseline and percent change/percent improvement from baseline will not be calculated.

A 2-sided significance level of 5% will be used for all analyses. Two-sided 95% confidence intervals will be calculated.

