11.8 Data Derivation

The following conversion factors will be used to convert days to months or years, where applicable:

- 1 month = 30.4375 days
- 1 year = 365.25 days.

See Section 12.2 for the calculation of subject age.

Duration will be calculated by the difference of start and stop date + 1 (eg AE duration (days) = stop date of AE – start date of AE + 1) (if not otherwise specified). Durations are calculated only when both dates are available (imputed dates cannot be used for the duration computation).

See Section 14 for the calculation of treatment duration.

The time since an event (eg time since first diagnosis) will be calculated as reference date minus date of event.

12 Trial Subjects

The subsections in this section include specifications for reporting subject disposition and treatment/study discontinuations. Additionally, procedures for reporting protocol deviations are provided.

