16.1 Adverse Events

Adverse events will be collected throughout the study and coded using version 19.1 of MedDRA or later.

Treatment-emergent adverse events (TEAEs) are those events that start on or after the day of first administration of study treatment. If an AE started on the same date as the first administration of the first study treatment given, the timing related to study treatment as recorded on the adverse events page of the eCRF will be taken into account when determining treatment emergence. A worst case approach will be used, ie if time is missing or if the AE occurred at the same time as the first administration of the first study treatment given, then the AE will be classified as treatment-emergent.

Incomplete AE-related dates will be handled as follows:

- In case the onset date is missing completely or missing partially but the onset month and year, or the onset year are equal to the start of study treatment then the onset date will be replaced by the minimum of start of study treatment and AE resolution date.
- In all other cases the missing onset day or missing onset month will be replaced by 1.
- Incomplete stop dates will be replaced by the last day of the month (if day is missing only), if not resulting in a date later than the date of subject's death. In the latter case the date of death will be used to impute the incomplete stop date.
- In all other cases the incomplete stop date will not be imputed.

Only TEAEs will be included in tables and will be summarized by treatment arm. All AEs will be listed.

Unless otherwise stated, TEAEs will be displayed in terms of frequency tables: primary SOC in alphabetical order, then PT in order of decreasing frequency across both treatment arms. If a subject has more than one event for a particular SOC or PT, then the event will be counted once only for the subject. For example, if a subject has two different TEAEs but these are within the same SOC, then they will be counted once for each PT but only once for the SOC. If at any time a summary is being prepared on data that are not fully coded, uncoded TEAEs will be summarized with a SOC as 'Uncoded' and the PT term will be set to the TEAE verbatim text.

If an AE is reported for a given subject more than once during treatment, the worst relationship to study treatment will be tabulated.

Adverse events related to study treatment are those events with relationship missing, unknown or yes.

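### Injection site reactions without a complete stop date get no duration, so the longest-reaction table can class a subject by a shorter reaction

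*SAP*

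**What the plan says.** SAP 11.4 refers the handling of missing dates and times for these reactions to SAP 16.1.1. That section plans a continuous summary of duration in hours, a grade-by-duration table, and this category display: "Number of subjects with duration of study drug related injection site reaction <24 hours, ≥ 24 < 48 hours and ≥ 48 hours". Where several study-drug-related reactions occur in one person, "then the event with the longest duration will be used".

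Missing times are filled in. A missing start time becomes 00:00, and for the other end "If stop time is missing then stop time will be set to 23:59". Missing dates are not filled in: "Duration will not be calculated if start date or stop date are missing".

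Two other SAP sections settle partial dates. SAP 16.1 imputes adverse event stop dates in one situation: "Incomplete stop dates will be replaced by the last day of the month (if day is missing only"). Otherwise an incomplete stop date is left as it is. SAP 11.8 then rules out using such a date here: "Durations are calculated only when both dates are available (imputed dates cannot be used for the duration computation").

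For categorical displays in general, SAP 11.1 asks for a count of subjects with missing data and adds: "Percentages will be based on the number of subjects with non-missing data in the analysis set of interest", unless otherwise specified.

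**The concern.** The display is meant to show how long each subject's worst reaction lasted. A reaction still present at last contact has lasted at least from onset to that contact, which will often be more than 48 hours. The plan discards that information. Such a reaction cannot be selected as the longest, so the subject is described by whichever shorter reaction happens to have complete dates. The missing count does not reveal this, because the subject has a value and is not missing.

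The other missing-data rules in the same section lean the opposite way. A start time of 00:00 and a stop time of 23:59 both lengthen a reaction, and the longest event is taken. The stop-date rule can only remove reactions from consideration.

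At stake is the accuracy of a planned local tolerability table in a trial that supports a new formulation. The sample size text (Protocol 8.1, SAP 7.1) names injection site reactions among the most common events of interest, with an expected incidence of 26.0%.

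**Working it through.** The plan gives no figure on this point to reproduce. The check applies the stated rule to simple cases and then shows how far a percentage could move.

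**Rule (SAP 16.1.1 with 11.8).** Duration in hours = stop date/time minus start date/time. A missing start time is set to 00:00 and a missing stop time to 23:59. If either date is missing or only imputed, there is no duration. Subject value = the largest duration that could be calculated. Cut points are 24 and 48 hours.

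**Cases.**

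| Subject's drug-related reactions | Calculated value | Category under the SAP |
|---|---|---|
| A. One unresolved | none | none; counted as missing |
| B. One unresolved, one resolved after 6 h | 6.0 h | <24 h |
| C. One unresolved, one resolved after 72 h | 72.0 h | ≥48 h |
| D. One, start and stop on consecutive days, both times missing | 47.98 h (00:00 to 23:59 next day) | 24 to <48 h |

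Case B is the misclassification: the subject has a value, and it comes from the shorter reaction. Case A loses its category and, under SAP 11.1, its place in the denominator. Case C is unharmed. Case D shows that missing times alone cause no loss; the problem is confined to missing or partial dates.

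A stop date known only to the month behaves like A or B, because SAP 16.1 would impute it and SAP 11.8 then bars its use.

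**Illustration of size.** The documents do not give the number of reactions without a complete stop date. Assume:
- 130 subjects per arm and 26.0% incidence (SAP 7.1): 130 × 0.26 = 33.8, about 34 subjects with a reaction;
- all of these reactions are drug-related, and the table is restricted to these subjects;
- 3 or 7 subjects have a resolved reaction of ≥48 h;
- 1 or 3 further subjects have an unresolved reaction that truly lasted ≥48 h, and no other reaction that long.

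| Resolved ≥48 h | Unresolved ≥48 h | All counted as ≥48 h | SAP, if unresolved are missing (case A) | SAP, if classed by a shorter reaction (case B) |
|---|---|---|---|---|
| 3 | 1 | 4/34 = 11.8% | 3/33 = 9.1% | 3/34 = 8.8% |
| 3 | 3 | 6/34 = 17.6% | 3/31 = 9.7% | 3/34 = 8.8% |
| 7 | 1 | 8/34 = 23.5% | 7/33 = 21.2% | 7/34 = 20.6% |
| 7 | 3 | 10/34 = 29.4% | 7/31 = 22.6% | 7/34 = 20.6% |

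The counts of 3, 7 and 1 are assumed. The table shows what each misplaced subject does to the percentage; it does not estimate how many there will be.

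**The case against.** The best defence is that very few reactions should lack a stop date. Protocol 7.4.2.2 asks for onset and resolution dates for each adverse event. Table 1, footnote t, asks patients to record when injection site pain at doses 3 to 5 resolves if it persists beyond 1 hour. Protocol 7.4.2.6 has adverse events assessed for final outcome at the 4-month visit, and SAP 8 provides data cleaning and a data review meeting before a single database lock. This stands, and it is why the effect is probably small.

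It can also be said that SAP 11.1 already requires a missing count, so a subject in case A remains visible in the output. That is correct; only the category and the denominator are lost. It does not help in case B.

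Keeping imputed dates out of durations is a deliberate convention, and it is sensible for a mean or median. It is less suitable for an open-ended top category, where a lower bound on the duration is enough to classify the subject.

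A reader might go further and infer that the comparison between arms is biased toward no difference, because the arm with more persistent reactions loses more of them. The documents do not support this. After Week 12 the visits up to Week 48 are 12 weeks apart, and for home doses the patient records "injection site reaction (yes/no) in a patient diary". Those features make poorly remembered dates of resolved reactions plausible, and such reactions may well have been short. They do not show that the missing stop dates belong mainly to long or unresolved reactions, or that they differ between arms.

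**Conclusion.** The point holds as a small improvement. Under SAP 16.1.1 and 11.8, a drug-related injection site reaction without a complete stop date has no duration. A subject who also has a shorter resolved reaction is then placed in too low a category, or in one the data cannot confirm. A subject with no other dated reaction is left in the missing count and outside the denominator. A subject with another resolved reaction of 48 hours or more is classed correctly.

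The effect is confined to the descriptive duration summaries, including grade by duration. The occurrence of injection site reactions, their rate per injection and the primary endpoint are unaffected, and all adverse events are listed. No hypothesis or decision rule uses the duration categories.

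The size cannot be estimated from the documents, because they give neither the frequency of incomplete stop dates nor the share of reactions lasting 48 hours or more. Nor can every missing stop date be read as a long reaction, since some will be resolved reactions whose date was not captured.

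**What to change.** In SAP 16.1.1, for the category tables only and as a stated exception to SAP 11.8:

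1. Count a reaction as ≥48 hours, and as the subject's longest, if it is recorded as ongoing and onset to last adverse event contact is at least 48 hours, or if the earliest date compatible with a partial stop date is at least 48 hours after onset. For example, onset on 28 May at 10:00 with a stop date of June gives at least 86 hours (to 1 June 00:00) and qualifies. Onset on 10 June with a stop date of June does not.
2. If a stop date is otherwise incomplete or wholly unknown, and the subject has no other reaction of ≥48 hours, show the subject in an ongoing/unknown row.
3. Use all subjects with a study-drug-related injection site reaction as the denominator.

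Leave the continuous duration summary on observed complete dates, so that minimum values running to weeks do not enter a mean in hours. Show beside it, by arm, the number of reactions without a duration.

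The cost is a few sentences in the SAP, a few lines of programming and one extra table row. No additional data collection is needed.

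### The injection-site-reaction latency summaries choose one reaction per subject by shortest duration, which is either unrelated to latency or leaves mixed-onset subjects out of the delayed categories

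*SAP*

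**What the plan says.** SAP 16.1.1 plans two sets of summaries for drug-related injection site reactions.

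- **How long the reaction lasted.** Duration is defined in hours as reaction stop minus reaction start. A subject with several reactions contributes the longest.
- **How long after dosing it began.** This is measured once from the first administration and once from the last, each with summary statistics and a count of subjects in three classes (under 24 h, 24 to under 48 h, 48 h or more). The second count is introduced as "Number of subjects with time since the last study treatment administration to the injection site reaction".

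For the onset summaries the selection rule appears four times, once for each statistic and each count: "If a subject has more than one study drug related injection site reactions then the event with the shortest duration will be used".

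Missing clock times are also dealt with there. For the dose, "If last study treatment administration time is missing then it will be set to 23:59". For the reaction, "If injection site reaction start time is missing then it will be set to 00:00". If any time is missing and both dates are the same, "then time since last study treatment administration will be set to 0".

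**The concern.** The rule uses *duration* in a place where the quantity being tabulated is latency, and the same list has already given *duration* a different meaning. Two programmers could follow the text and produce different tables.

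Neither reading gives a useful count. On one, the onset time shown for a subject is decided by how briefly a reaction lasted. On the other, the two later classes in the table of time since last administration hold only subjects who never had an earlier reaction. The SAP created those classes, and a reader of the report will take them as the number of subjects per arm with delayed reactions. With 25 planned doses per subject (Week 0 to Week 48, every second week), repeat reactions are possible, so the choice of event is not a formality.

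**Working it through.** The documents give no figure for this rule, so there is nothing to reproduce. The check applies the rule to cases and then to a simple model.

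**1. Worked cases.** One subject has two reactions, one starting 1 h after its dose and one starting 60 h after its dose.

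| Reaction at 1 h lasted | Reaction at 60 h lasted | Class if briefest reaction is kept | Class if shortest latency is kept |
|---|---|---|---|
| 72 h | 12 h | 48 h or more | under 24 h |
| 12 h | 72 h | under 24 h | under 24 h |

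On the literal reading the same pair of onset times lands in different classes depending only on how long each reaction lasted. On the latency reading the reaction at 60 h is never shown.

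**2. Size on the shortest-latency reading.** Inputs: k reactions per subject, and a share q of reactions starting at 24 h or later, independent within subject. Both are assumptions; the documents give neither.

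- Subjects with any delayed reaction: 1 − (1 − q)^k
- Subjects shown as delayed: q^k

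To scale this, SAP 7.1 and Protocol 8.1 plan 130 subjects per arm and an injection-site-reaction incidence of 26%, so 0.26 × 130 = 33.8, about 34 affected subjects per arm.

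| q | k | Any delayed | Shown as delayed | Of 34: any / shown |
|---|---|---|---|---|
| 0.1 | 1 | 10% | 10% | 3.4 / 3.4 |
| 0.1 | 2 | 19% | 1% | 6.5 / 0.3 |
| 0.2 | 1 | 20% | 20% | 6.8 / 6.8 |
| 0.2 | 2 | 36% | 4% | 12.2 / 1.4 |
| 0.2 | 3 | 48.8% | 0.8% | 16.6 / 0.3 |
| 0.4 | 2 | 64% | 16% | 21.8 / 5.4 |
| 0.4 | 3 | 78.4% | 6.4% | 26.7 / 2.2 |

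Positive correlation within subject narrows the gap. With one reaction per subject there is none.

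**3. Size on the literal reading.** If how long a reaction lasts is independent of its latency (assumption), the kept reaction is in effect a random one, so the share shown as delayed is q. With q = 0.2 and k = 2 that is 20% against a true 36%. Among subjects with one immediate and one delayed reaction, the delayed one is dropped in half of cases and the immediate one in the other half.

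**4. Time since first administration.** Keeping the earliest onset is an ordinary time-to-first-event summary. On the literal reading the rule does not deliver it, because the briefest reaction need not be the earliest.

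**5. Missing times.** Take a 09:00 dose and a reaction dated the next day with no start time. The rule gives 15 h; the true value lies between 15 and 39 h. With both times missing, a next-day reaction gets 0.02 h (true range 0 to 48 h), and one dated three days later gets 48.02 h (true range 48 to 96 h), which stays in the top class. The shift is always downward, by at most about 24 h per missing time.

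**The case against.** The strongest reply is that this is a wording slip in supportive, descriptive tables and that no event is lost from the report. Much of that stands. The primary analysis (SAP 15.1) counts subjects with hypersensitivity events and does not use latency. SAP 16.1 lists all adverse events. SAP 16.1.1 adds a reaction rate per injection and a table by grade and time since last administration, for which no shortest-event rule is written. SAP 16.6 tabulates reactions by antibody status. None of these, however, assures an arm-level count of subjects with delayed reactions. The grade table may fall under the once-per-subject counting rule of SAP 16.1, and the plan does not say which onset time would then be used.

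A reader might infer more than the documents support.

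- *Delayed reactions vanish for every subject who also had an immediate one.* That follows only on the shortest-latency reading. On the literal reading the immediate reaction may be the one dropped.
- *Delayed reactions are the key category for hypersensitivity or immunogenicity, so a formulation difference would be hidden.* The plan defines hypersensitivity by a narrow standardised query with no latency element. Protocol 3.3 links immunogenicity to injection site reactions without mentioning delay. No between-arm effect has been shown.
- *The missing-time rules hide delayed reactions.* They delete nothing and act only when a clock time is missing. The home diary records the reaction only as present or absent ("location of administration, and injection site reaction (yes/no) in a patient diary"), but the same section of the Protocol (6.8) asks for the time of dosing, and Protocol 7.4.2.2 asks for onset times where timing relative to the dose matters.
- *Keeping the shortest interval is the wrong direction because the duration summaries keep the longest.* Each can be called conservative: the longest-lasting reaction, and the closest link in time to the drug.

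**Conclusion.** The selection rule is wrong as written. Read literally, it tabulates an onset time chosen by an unrelated property of the reaction. Read as shortest latency, it makes the two later classes of the time-since-last-administration table mean that no reaction came earlier, and a mixed-onset subject is not counted as delayed.

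The effect is limited to these descriptive latency summaries. Its size depends on the number of reactions per subject and the delayed share, which the documents do not give. Over the assumed range shown, it runs from no loss (one reaction each) to roughly 6 to 24 of about 34 affected subjects per arm on the shortest-latency reading (6.5 − 0.3 = 6.2; 26.7 − 2.2 = 24.5), with independence within subject as an upper-end assumption. The handling of missing times is a secondary matter and does not need to change for this point.

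**What to change.** Amend SAP 16.1.1 as follows.

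- For time since first administration, replace shortest duration with earliest onset, in both the statistics and the class counts.
- For time since last administration, state that latency runs from the most recent dose before the reaction. SAP 14 uses last dose for the final dose in the study, so the term needs fixing here.
- Tabulate that latency per reaction, and count each subject once in every latency class in which he or she had a reaction.

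The cost is SAP wording and limited reprogramming of safety tables. The downside is that a subject with several reactions can appear in more than one class, so the classes no longer add up to the number of subjects; a footnote should say so.
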